### 5.3.2. Covariates

The list of demographic and clinical characteristics considered for descriptive reporting, subgroups and inclusion as covariates in models for generating the propensity scores are provided in Table 5.3. The Komodo Health database will be source of all variables.

Patients will be considered to have a comorbidity or hospitalization during baseline if there was evidence of a diagnosis at any time during the baseline period. Evidence of comorbidities or hospitalization during follow-up will be considered as new diagnoses. Once diagnosed, patients will be considered diagnosed for the remainder of their follow-up. ART adherence during baseline and follow-up will be updated every 6 months (180 days) based on the data collected in that previous timeframe. For baseline annual physical exam and annual influenza vaccine, patients will be considered adherent (coded as 'Yes') if there was evidence of these events at any time during the baseline period. During the follow-up, patients will be considered adherent up to 365 days after the last event date.

For annual CD4 and viral load laboratory tests during baseline and follow-up, patients will be coded as 'Yes' up to 365 days after the last event date. For respiratory virus season during follow-up, patients will be coded as 'Yes' if the observation time is in October, November, December, January, February, March or April.

The baseline period for the assessment of covariates is the six months prior to the index date, i.e., no data prior to six months will be included.

Covariates used at baseline only will be considered time-fixed confounders. Covariates additionally or only used during follow-up will be considered time-varying confounders.

Categories may be collapsed, or covariates may be excluded from the propensity scores if models fail to converge.

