#### **5.8.4. Inverse Probability of Treatment Weighting for Time-Varying Exposures**

Except for patients vaccinated more than 13 days before the end of the baseline period, exposure (vaccination) status will not be fixed at start of follow-up, with patients able to receive PCV13 during follow-up. Therefore, PCV13 will be considered a time-varying exposure. The values for some clinical characteristics may also change during the study period and values during baseline may be poor proxies for covariate values at the various points during the follow-up. Therefore, some covariates will be treated as time-varying confounders (Section 5.3.2).

Inverse probability of treatment weighting (IPTW) will be generated from predicted probabilities of vaccination status (propensity scores) to create pseudo-populations where any imbalances in the potential confounders by vaccination status are reduced. For the analyses of first events, stabilized weights will be generated for each patient for the baseline period and every 30 days from index during the follow-up until the earliest of the following: outcome, death, end of health plan enrollment or end of study period. For the analyses of recurrent events, stabilized weights will be generated for each patient for the baseline period and every 30 days from index during the follow-up until the earliest of the following: death, end of health plan enrollment or end of study period. This aims to make vaccination status independent of the measured confounders at each of the follow-up timepoints [9]. The weights will be used to estimate the average treatment effect (ATE). For the analysis of RZV, stabilized weights will be generated every 90 days instead of 30, due to the expected lower numbers of patients vaccinated with RZV overall and in each interval.

The numerators for the stabilized weights will be the estimated probability of a patient's observed vaccination status at timepoint given their prior vaccination status and time-fixed covariates. The denominators will be the estimated probability of a patient's observed vaccination status at the given timepoint given their prior vaccination status, time-fixed covariates and time-varying covariates. Numerators and denominators after vaccination will be set to 1 and the cumulative product of these ratios will be calculated, therefore IPT

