#### **5.8.7. Vaccine Effectiveness**

Crude PCV13 VE percentages will be estimated based on  $(1-HR) \times 100$ , where HR is obtained from unadjusted Cox models for first episodes for each outcome. VE percentages will also be obtained from marginal structural Cox models (Cox-MSM) after applying the IPT and the IPT\*IPC weights. As the numerators for the stabilized weights will include the index-fixed covariates, those covariates will also be included in the Cox-MSM for the outcomes [9]. Cluster robust standard errors will be used to account for the multiple records per patient. The proportional hazards assumption will be assessed graphically with the inspection of Schoenfeld residuals.

To explore potential changes in VE over time, HRs may also be generated during specific time periods using piecewise Cox models. The time periods will be 0-3 years (0 to 1079 days), 3-5 years (1080 to 1799 days), 5-7 years (1800 to 2549 days).

VE may also be assessed for recurrent events using the Andersen-Gill (AG) model [11]. For each outcome, subsequent events will be of the same type, e.g., in the analysis of IPD it will be assumed that a patient is only at risk for future IPD events. The VE is assumed constant across the recurrent events.

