### 7.2.2. Code for Generating IPTW and IPCW

```
library(ipw)
iptw <- ipwtn(exposure = pcv13, family = "survival",
numerator = ~ x1 + x2 + ... + xn, denominator = ~ x1 + x2 + ... + xn + xt1 + xt2 + ... + xtn,
id = ptid, tstart = tstart, timevar = tstop, type = "first",
data = ipdfirst)
ipcw <- ipwtn(exposure = censor, family = "survival",
numerator = ~ x1 + x2 + ... + xn, denominator = ~ x1 + x2 + ... + xn + xt1 + xt2 + ... + xtn,
id = patient, tstart = tstart, timevar = tstop, type = "cens",
data = ipdfirst)
iptw.stab<-iptw$ipw.weights
ipcw.stab<-ipcw$ipw.weights
ipdfirst<-cbind(ipdfirst, iptw.stab, ipcw.stab)
ipdfirst$comb.weights<- ipdfirst$iptw.stab*ipdfirst$ipcw.stab

#Plot of stabilized weights during follow-up in unvaccinated
ipwplot(weights = subset(ipdfirst$iptw, ipdfirst$pcv13==0),
subset(timevar = ipdfirst$tstop, ipdfirst$pcv13==0),
binwidth = 183, ylim = c(-1.5, 1.5), main = "Stabilized weights",
xlab = "Years Since Index", ylab = "Logarithm of Stabilized IPTW",
xaxt = "n", yaxt = "n")
axis(side = 1, at = seq(0, 15, 1), labels = as.character(seq(0, 15, 1)*0.5))
axis(side = 2, at = c(-1.5, -1, -0.5, 0, 0.5, 1, 1.5),
labels = as.character(c(-1.5, -1, -0.5, 0, 0.5, 1, 1.5)))
```

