### 7.2.5. Code for Cox Models

```
#Code is the same for first event and recurrent events (Andersen-Gill) models
#Crude overall
library(survival)
crude.cox<-coxph(Surv(tstart, tstop, ipd) ~ pcv13 + cluster(ptid), data = ipdfirst)
```

```
#IPT weighted overall
iptw.cox<-coxph(Surv(tstart, tstop, ipd) ~ pcv13 + x1 + x2 + cluster(ptid),
                  data = ipdfirst), weights = iptw.stab
```

```

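### Index-date values of 27 covariates are adjusted only through the weight denominators: without truncation this costs some precision, and optional truncation would let part of the baseline confounding back in

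*SAP*

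**What the plan says.** SAP 5.3.2 sorts covariates by when they are used. On one side, "Covariates used at baseline only will be considered time-fixed confounders"; on the other, "Covariates additionally or only used during follow-up will be considered time-varying confounders". Applied to Table 5.3, the first rule leaves seven time-fixed covariates: age, sex, SVI, region, payor, year of HIV diagnosis and baseline pneumonia. Another 27 variables with a covariate role are used at baseline and in follow-up, so they are time-varying. They are the comorbidities, smoking, immunosuppressive medication, opportunistic infections, hospitalization, ART adherence, physical exam, influenza vaccine, and CD4 and viral load testing.

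Under SAP 5.8.4 the weight numerator is the probability of the observed "status at timepoint given their prior vaccination status and time-fixed covariates". The code in 7.2.2 agrees: "numerator = ~ x1 + x2 + ... + xn", with the time-varying terms in the denominator only, for IPTW and IPCW alike. SAP 5.8.7 carries the same set into the outcome model: "As the numerators for the stabilized weights will include the index-fixed covariates, those covariates will also be included in the Cox-MSM for the outcomes". The code in 7.2.5 fits "Surv(tstart, tstop, ipd) ~ pcv13 + x1 + x2 + cluster(ptid".

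Three further provisions matter. SAP 5.8.4 permits truncation at the 1st and 99th percentiles by judgement. SAP 5.8.5 permits, but does not require, adding variables with a weighted SMD above 0.1 to the outcome model. Protocol 9.7 lists hospitalization both as a time-fixed baseline covariate and as a time-varying one, whereas SAP Table 5.3 read with 5.3.2 makes it time-varying only.

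**The concern.** A stabilized weight is least variable when the numerator contains everything known at baseline and the outcome model conditions on the same terms. Here the numerator leaves out the index-date values of most clinical covariates, so the weights must remove the whole baseline difference in those covariates as well as the differences that develop later. Weights are held constant after vaccination, so a large weight set at or near index stays on all of that person's vaccinated follow-up.

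Two things are at stake. One is precision, which is thin for IPD in the shorter window and in subgroups: the Protocol Table 2 lower limits at VE 22.5% and 36 months are 3% and 2%, and the SAP Table 5.1 lower limit at 58,000 people is 1%. The other is sensitivity to truncation. Cutting the extreme weights undoes part of the baseline adjustment, and by default the outcome model has no index-date terms to make up for it.

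**Working it through.** **Reference figure.** The documents give no figure for weight variability or truncation. The nearest is Protocol Table 2 (IPD, VE 22.5%, 97 months, 4% censoring): CI 11 to 33% with 1,452 events, from Cox models with no weighting mentioned. It implies SE = [ln 0.89 − ln 0.67] / 3.92 = 0.072. An approximate recalculation gives 2,101 events and CI 11.5 to 32.1 if everyone is followed for 97 months, and 1,210 events and CI 8.1 to 34.6 with staggered uniform entry. The stated count lies between. Entry and vaccination timing are not given, so it cannot be reproduced exactly and is not called wrong.

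**Simulation.** Inputs from the documents: 32% vaccinated, IPD incidence 183 per 100,000, VE 22.5%, 4% annual censoring, 30-day intervals. Assumed: six binary covariates with associations of the sizes below, acting so that the vaccine looks better than it is. There were 60,000 people and three seeds, with SEs scaled to 175,000. Pooled-logistic weights and a weighted Poisson model with time strata stood in for the SAP's Cox models. *Plan* uses only the time-fixed set. *Fix* adds index-date values to numerator, denominator and outcome model.

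| Assumed confounding | Weak | Moderate | Strong |
|---|---|---|---|
| log OR, vaccination / log HR, outcome | 0.2 / 0.4 | 0.4 / 0.6 | 0.7 / 0.8 |
| Weight SD in vaccinated, plan → fix | 0.19 → 0.13 | 0.39 → 0.26 | 0.76 → 0.47 |
| 1 + CV² in vaccinated, plan → fix | 1.04 → 1.02 | 1.15 → 1.06 | 1.58 → 1.22 |
| SE(log HR), plan larger by about | 1% | 3.5% | 13% |
| VE without weights (true 22.5) | 26.1 | 32.6 | 42.0 |
| VE, plan, untruncated | 22.5 | 22.7 | 22.1 |
| VE, plan, truncated 1/99 | 22.8 | 23.8 | 25.7 |
| Truncation shift, plan | +0.3 | +1.1 | +3.6 |
| Truncation shift, fix | +0.2 | +0.7 | +2.0 |
| Largest SMD after truncation, plan | 0.015 | 0.03 | 0.06 |

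The SE ratios are 0.0599/0.0579 = 1.035 (moderate) and 0.0649/0.0575 = 1.13 (strong).

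**Share of confounding returned by truncation** = (truncated − untruncated) / (unweighted − untruncated): 0.3/3.6 = 8% (9% before rounding), 1.1/9.9 = 11%, 3.6/19.9 = 18%. The part due to this choice is the plan's shift minus the fix's shift: 0.1, 0.4 and 1.6 points.

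**What the SE ratio means for the limits.** Take the stated intervals as illustration and scale the lower half-width on the log scale.

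- Full cohort: ln 0.89 − ln 0.775 = 0.138. Times 1.035 the lower limit is 10.6%; times 1.13 it is 9.4%, against 11%.
- 58,000 people (SAP Table 5.1): ln 0.99 − ln 0.775 = 0.245. Times 1.035 gives about 0.1%; times 1.13 gives about −2%, against 1%.

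**Other simulations.** One with ten assumed covariates and 30-day intervals agreed on the mechanism: under moderate to strong confounding the fix cut the SE by about 2 to 4%, and weight SD in the vaccinated fell from 0.37–0.55 to 0.22–0.34. There truncation moved the planned VE down, to between 19.9 and 21.6, and left it near 22.6 after the fix. The direction of the shift therefore depends on the direction of the confounding. A coarser one with half-year intervals gave planned SEs about 3% and 7% larger (0.0485 v 0.0470; 0.0513 v 0.0479).

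**The case against.** The planned scheme is a valid marginal structural model. A reader might infer that it leaves baseline confounding uncontrolled. It does not: the denominators contain these covariates, and the untruncated planned VE averaged 22.1 to 22.7 against a true 22.5.

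A reader might also infer that any truncation restores baseline confounding with nothing to absorb it. That goes too far. Truncation is optional, it returned 9 to 18% of the confounding removed, and it also shifts the repaired analysis because later confounding is truncated too. SAP 5.8.5 does give a route into the outcome model. What remains of the point is that this route is discretionary. No SMD after truncation exceeded 0.06, so it would not have been triggered, and the example balance code in 7.2.4 uses the untruncated `iptw.stab`.

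Two further claims would outrun the documents. One is that the index value carries most of the information. Comorbidities and hospitalization do stay positive once coded, but ART adherence is revised every 180 days, and exam, influenza vaccine and test status lapse after 365 days. The other is that IPD suffers most: outcomes were not compared, and IPD simply has less precision to spare.

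The fix also has a statistical cost. It moves baseline control onto the outcome model's form. Untruncated, it averaged 21.6 (moderate) and 20.4 (strong), against 22.7 and 22.1 under the plan. This objection stands, though it rests on three seeds.

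**Conclusion.** The point holds as a cheap improvement, not as an error that invalidates the analysis. Without truncation the cost is efficiency only: an SE about 1 to 4% larger under weak to moderate confounding and up to about 13% under strong. With 1st/99th percentile truncation, VE moves by about 0.3 to 3.6 points under the plan, of which 0.1 to 1.6 points are due to this choice, and the SMD rule may not catch it. If the true associations are weak, the matter is minor.

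These sizes rest on assumed covariate associations that the documents do not supply, on correctly specified weight models, and on discrete-time analogues of the planned Cox models. The mismatch on hospitalization between Protocol 9.7 and SAP Table 5.3 needs an edit in any case.

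**What to change.** - **SAP 5.3.2, 5.8.4, 5.8.7, 7.2.2, 7.2.5:** define the index-date value of each covariate used at baseline and in follow-up as an additional time-fixed term. Put it in the numerators and denominators of IPTW and IPCW and in the Cox-MSM. Keep updated values in the denominators only. Collapse or drop rare ones under the convergence rule already in 5.3.2.
- **SAP 5.8.5 and 7.2.4:** compute SMDs with the weights actually used in the outcome model, truncated if truncation is applied.
- **SAP 5.8.4 and 5.8.11:** report untruncated and truncated results side by side.
- **Protocol 9.7 and SAP Table 5.3:** reconcile the status of hospitalization.

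The data are already collected, so the work is programming. The HR becomes conditional on more baseline covariates. With ART adherence in three categories, 27 covariates add about 28 parameters to about 25. With 1,224 IPD events (the lowest 97-month count) that is 1,224/53 = 23 events per parameter; with 752 (the lowest 36-month count) it is 14. In a subgroup of 58,000 it is about 9 (1,452 × 58,000/175,000 = 481 events; 481/53), so collapsing will matter there. The untruncated VE may shift by about 0.5 to 2 points if confounding is moderate to strong, which is a further reason to show both versions.

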**Table 5.3 List of Covariates**

Variable	Operational Definition	Role	Time of Use
Age in years	Calculated as [year individual meets HIV criteria] – [birth year]  Categorized as: 18-49, 50-64, 65-74, and $\geq 75$ years  As a subgroup, age will be categorized as 18-49, 50-64 and 65+ years	Descriptive (continuous and categorical)  Covariate (categorical)  Subgroup (categorical)	Baseline
Sex	Male, Female, Other/ Unknown	Descriptive, covariate	Baseline
Social Vulnerability Index (SVI)	SVI characterizes resiliency of a community when faced by external pressures and stresses[6, 7]. SVI ranges from 0 to 100, where a value of 100 indicates the most vulnerable population.  3-digit zip codes will be translated to 3-digit zip code tabulation areas, and SVI will be calculated at the 3-digit zip code tabulation area.  Categorized as: low (lowest quartile), average (middle two quartiles) and high (highest quartile).	Descriptive, covariate	Baseline
US region	Northeast, North Central, South, West, Unknown	Descriptive, covariate	Baseline

Payor	Commercial, Dually eligible, Medicaid/CHIP, Medicare, Missing, Other	Descriptive, covariate	Baseline
Year of HIV diagnosis	Calendar year of first HIV diagnosis code 2014, 2015, 2016, 2017, 2018, 2019, 2020, 2021.  When used as a subgroup year will be categorized as 2014, 2015-2016, 2017-2018, 2019-2021.	Descriptive, covariate, subgroup	Baseline
Alcoholism	ICD-9-CM or ICD-10-CM codes listed in Appendix Protocol Annex Table 1.1 Yes, No	Descriptive, covariate	Baseline and follow-up
Asplenia	CPT/Healthcare Common Procedure Coding System (HCPCS), ICD-10-Procedure Coding System (ICD-10-PCS), ICD-9-Procedure Coding System (ICD-9-PCS), ICD-9-CM, or ICD-10-CM codes listed in Protocol Annex Table 1.2	Descriptive, covariate	Baseline and follow-up
Chronic heart disease	CPT/HCPCS, ICD-10-PCS, ICD-9-PCS, ICD-9-CM, or ICD-10-CM codes listed in Protocol Annex Table 1.4 Yes, No	Descriptive, covariate	Baseline and follow-up
Chronic kidney disease and renal failure	CPT/HCPCS, ICD-10-PCS, ICD-9-PCS, ICD-9-CM, or ICD-10-CM codes listed in Protocol Annex Table 1.5 Yes, No	Descriptive, covariate	Baseline and follow-up
Chronic liver disease	CPT/HCPCS, ICD-10-PCS, ICD-9-PCS, ICD-9-CM, or ICD-10-CM codes listed in Protocol Annex Table 1.6 Yes, No	Descriptive, covariate	Baseline and follow-up
Chronic lung disease	ICD-9-CM or ICD-10-CM codes listed in Protocol Annex Table 1.7 Yes, No	Descriptive, covariate	Baseline and follow-up
Asthma	ICD-9-CM or ICD-10-CM codes listed in Protocol Annex Table 1.3 Yes, No	Descriptive, covariate	Baseline and follow-up
Diabetes mellitus	ICD-9-CM or ICD-10-CM codes listed in Protocol Annex Table 1.9 Yes, No	Descriptive, covariate	Baseline and follow-up
Generalized malignancy	CPT/HCPCS, ICD-10-PCS, ICD-9-PCS, ICD-9-CM or ICD-10-CM codes listed in Annex Table 1.10	Descriptive, covariate	Baseline and follow-up
Immunosuppressive medications	PLWH will be considered on immunosuppressive medications if: 1) ≥1 NDC, HCPCS, or ICD-10-PCS code in Appendix Table 7.7	Descriptive, covariate	Baseline and follow-up

	2) ≥ 1 NDC (using oral only) in Appendix Table 7.7 where the daily dose is ≥ 20mg or prednisone or prednisone equivalent for a duration of ≥14 consecutive days Yes, No		
Leukemia	ICD-9-CM or ICD-10-CM codes listed in Protocol Annex Table 1.12	Descriptive, covariate	Baseline and follow-up
Multiple myeloma	ICD-9-CM or ICD-10-CM codes listed in Annex Table 1.13	Descriptive, covariate	Baseline and follow-up
Nephrotic syndrome	ICD-9-CM or ICD-10-CM codes listed in Protocol Annex Table 1.14 Yes, No	Descriptive, covariate	Baseline and follow-up
Non-Hodgkin's lymphoma	ICD-9-CM or ICD-10-CM codes listed in Protocol Annex Table 1.15	Descriptive, covariate	Baseline and follow-up
Organ transplant	CPT/HCPCS, ICD-10-PCS, ICD-9-PCS, ICD-9-CM or ICD-10-CM codes listed in Protocol Annex Table 1.16	Descriptive, covariate	Baseline and follow-up
Sickle cell disease or other hemoglobinopathies	ICD-9-CM or ICD-10-CM codes listed in Protocol Annex Table 1.17 Yes, No	Descriptive, covariate	Baseline and follow-up
Hepatitis B	ICD-9-CM or ICD-10-CM codes listed in Protocol Annex Table 2.1 Yes, No	Descriptive, covariate	Baseline and follow-up
Hepatitis C	ICD-9-CM or ICD-10-CM codes listed in Protocol Annex Table 2.2 Yes, No	Descriptive, covariate	Baseline and follow-up
Cigarette smoking	ICD-9-CM or ICD-10-CM codes listed in Protocol Annex Table 1.7 Yes, No	Descriptive, covariate	Baseline and follow-up
Annual physical exam	CPT/HCPCS codes listed in Protocol Annex Table 3.1 Yes, No	Descriptive, covariate	Baseline and follow-up
Annual influenza vaccine	CPT/HCPCS, ICD-10-PCS, ICD-9-PCS, or NDC codes listed in Appendix Table 7.8 Yes, No	Descriptive, covariate	Baseline and follow-up
Any pneumonia infection	ICD-9-CM or ICD-10-CM codes listed in Appendix Table 7.4 Yes, No	Descriptive, covariate	Baseline
Any hospitalization	Evidence of inpatient claim(s) Yes, No	Descriptive, covariate	Baseline and follow-up
Hodgkin's lymphoma	ICD-9-CM or ICD-10-CM codes listed in Protocol Annex 1.11 Yes, No	Descriptive, covariate	Baseline and follow-up
Opportunistic infections	ICD-9-CM or ICD-10-CM codes listed in Protocol Annex Table 14	Descriptive, covariate	Baseline and follow-up

	Yes, No  Note: In the analysis of all-cause pneumonia, pneumocystis jirovecii pneumonia codes are excluded from the follow-up. In the analysis of candidiasis negative control outcomes, candidiasis infection codes are excluded from the follow-up.		
Antiretroviral treatment (ART) adherence	ART use will be identified by NDC codes listed in Appendix Table 7.2  Adherence will be measured as 'Proportion of days covered = (Number of days covered by any ART, excluding ritonavir and cobicistat) ÷ (total days)*100'[8] every six months  Individuals with >80% of days covered will be classified as 'adherent' and individuals with ≤80% of days covered will be classified as 'non-adherent'[8]. Individuals without ART information will be classified as Missing. As a subgroup, ART adherence will be calculated using the information over the entire follow-up.	Descriptive, covariate, subgroup	Baseline and follow-up
CD4 cell count	Categorized as <200, 200-499, ≥500 cells/mm 	Descriptive, subgroup	Baseline and follow-up
PPSV23 vaccination	NDC and CPT codes listed in Appendix Table 7.9  Yes, No. 0, 1, 2+ doses	Descriptive, subgroup	Before first HIV diagnosis, baseline and follow-up
Annual CD4 laboratory test	CD4 laboratory tests will be identified by CPT codes listed in Appendix Table 7.11  Individuals who have at least one CD4 laboratory test performed during each year of follow-up Yes, No	Covariate	Baseline and follow-up
Annual viral load laboratory test	Viral load laboratory tests will be identified by CPT codes listed in Appendix Table 7.12  Individuals who have at least one viral load laboratory test performed during each year of follow-up Yes, No	Covariate	Baseline and follow-up

Respiratory virus season	Respiratory virus season occurs between October 1 and April 30 Yes, No	Covariate	Follow-up
--------------------------	---	-----------	-----------

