9.3. Variables

Table 1. Variables, definitions, and measurement periods

Variable type	Variable	Definition	Measurement period
Exposure	PCV13 vaccination	Current procedural terminology® (CPT) codes and National Drug Codes (NDC) listed in Appendix Table 3	Follow-up
Primary outcomes	IPD	ICD-9-CM or ICD-10-CM codes listed in Appendix Table 4	Follow-up
	Pneumococcal pneumonia	ICD-9-CM or ICD-10-CM codes listed in Appendix Table 4	Follow-up
	All-cause pneumonia	ICD-9-CM or ICD-10-CM codes listed in Appendix Table 4	Follow-up
	Pneumococcal pneumonia or pneumonia with unspecified causes	ICD-9-CM or ICD-10-CM codes listed in Appendix Table 5	Follow-up
	Pneumonia with unspecified causes	ICD-9-CM or ICD-10-CM codes listed in Appendix Table 5	Follow-up
Covariates	Age	Calculated as [year individual meets HIV criteria] – [birth year] Categorized as 18-49, 50-64, 65-74, and ≥ 75 years	Baseline
	Sex	Male, Female, Other, Unknown	Baseline
	Social Vulnerability Index (SVI)	SVI characterizes resiliency of a community when faced by external pressures and stresses [25, 26]. SVI ranges from 0 to 100, where a value of 100 indicates the most vulnerable population. SVI will be estimated using zip code and will be categorized as low (lowest quartile), average (middle two quartiles) and high (highest quartile).	Baseline
	Payor	Medicaid/CHIP, Medicare, Commercial, Dually eligible, Other, Unknown	Baseline
	US region	Northeast, North Central, South, West, Unknown	Baseline

Variable type	Variable	Definition	Measurement period
	Index year	Calendar year of first HIV diagnosis code	Baseline
	Alcoholism	ICD-9-CM or ICD-10-CM codes listed in Annex Table 1.1	Baseline and follow-up
	Asplenia	CPT/Healthcare Common Procedure Coding System (HCPCS), ICD-10-Procedure Coding System (ICD-10-PCS), ICD-9-Procedure Coding System (ICD-9-PCS), ICD-9-CM, or ICD-10-CM codes listed in Annex Table 1.2	Baseline and follow-up
	Asthma	ICD-9-CM or ICD-10-CM codes listed in Annex Table 1.3	Baseline and follow-up
	Chronic heart disease	CPT/HCPCS, ICD-10-PCS, ICD-9-PCS, ICD-9-CM, or ICD-10-CM codes listed in Annex Table 1.4	Baseline and follow-up
	Chronic kidney disease and renal failure	CPT/HCPCS, ICD-10-PCS, ICD-9-PCS, ICD-9-CM, or ICD-10-CM codes listed in Annex Table 1.5	Baseline and follow-up
	Chronic liver disease	CPT/HCPCS, ICD-10-PCS, ICD-9-PCS, ICD-9-CM, or ICD-10-CM codes listed in Annex Table 1.6	Baseline and follow-up

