9.7. Data Analysis

Cox proportional hazards models will be used to estimate the hazard ratio (HR) for each outcome comparing vaccinated PLWH with unvaccinated (no PCV13) PLWH. To explore potential changes in VE over time, HRs will also be generated during specific time periods (0-3, 3-5, 5-7 years of follow-up) using piecewise Cox regression models, if there is adequate sample size. All models will be adjusted for time-fixed and time-varying covariates of interest using inverse probability of treatment weighting. The time-fixed covariates of interest include sex, age, payor, SVI, previous pneumonia infection, and hospitalization and will be measured during the baseline period. The time-varying covariates include risk factors for pneumonia (alcoholism, asplenia, asthma, chronic heart disease, kidney, liver, and lung diseases, cigarette smoking, diabetes, immunosuppressive conditions and medications, and sickle cell disease), annual physical exams, annual influenza vaccine, hospitalization, opportunistic infections, ART adherence, annual CD4 and viral load laboratory tests, and an indicator for respiratory virus season.

VE will be calculated as 1 minus the estimated HR for each outcome.

We will conduct two sets of analyses for each outcome. In the first set, we will examine the first event for each outcome and in the second set, all recurrent outcome events during follow-up will be included. In the first set of analyses, unvaccinated (no PCV13) PLWH will be followed from index date until the earliest occurrence of the following: outcome, PCV13 vaccination, death, end of health plan enrollment, or end of study period, and vaccinated PLWH will be followed from 14 days after vaccination date, or index date if vaccinated during the baseline period, until the earliest occurrence of outcome, death, end of health plan enrollment, or end of study period. In the second set of analyses unvaccinated (no PCV13) PLWH will be followed from index date until the earliest occurrence of PCV13 vaccination, death, end of health plan enrollment or end of study period and vaccinated PLWH will be followed from 14 days after vaccination date, or index date if vaccinated during the baseline period, until earliest occurrence of death, end of health plan enrollment, or end of study period.

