### **5.2.1. Inclusion Criteria**

- 1. HIV infection defined as at least one inpatient International Classification of Diseases, Ninth Revision, Clinical Modification (ICD-9-CM) or International Classification of Diseases, Tenth Revision, Clinical Modification (ICD-10-CM) code related to HIV (Appendix Table 7.1) or ≥2 outpatient ICD-9-CM or ICD-10-CM codes at least 30 days, but no more than 730 days, apart during January 1, 2014 and December 31, 2021*

*AND*

- 2. At least 18 years of age at the time of the first recording of HIV-related ICD-9-CM or ICD-10-CM code*

*AND*

- 3. At least six months of continuous enrollment in medical and pharmacy plans after the first HIV-related ICD-9-CM or ICD-10-CM code between January 1, 2014 and December 31, 2021. A gap of 30 days or less in enrollment will be allowed during this six month period.*

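### Age is adjusted only in four fixed baseline bands, one of them 32 years wide (18–49), although age in years is available

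*SAP*

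**What the plan says.** SAP Table 5.3 derives age in whole years from a calendar-year difference ("Calculated as [year individual meets HIV criteria" less birth year) and gives it three roles. It is "Descriptive (continuous and categorical") for description but "Covariate (categorical") for adjustment, in the bands "Categorized as: 18-49, 50-64, 65-74, and" 75 or over. Protocol Table 1 agrees: "Categorized as 18-49, 50-64, 65-74, and ≥ 75 years". For subgroups the top two bands are merged and the first is unchanged: "As a subgroup, age will be categorized as 18-49, 50-64 and 65+ years".

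Age is fixed at baseline. Protocol 9.7 states: "The time-fixed covariates of interest include sex, age, payor, SVI, previous pneumonia infection, and hospitalization". Under SAP 5.8.4 the time-fixed covariates enter both the numerator and the denominator of the stabilized weights. Under SAP 5.8.7 they also enter the Cox-MSM.

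SAP 5.3.2 lets categories be collapsed if models do not converge; nothing lets them be refined. SAP 5.8.5 computes standardized mean differences (SMDs) on the covariates. The one named sensitivity analysis (Protocol 9.7) changes the pneumonia definition, not the coding of age.

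**The concern.** A banded term treats everyone in a band as the same age. In the first band an 18-year-old and a 49-year-old are exchangeable as far as the model knows. If vaccination and pneumonia risk both vary with age between 18 and 49, the vaccinated and unvaccinated in that band differ in risk for a reason that the age term cannot remove.

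The rest of the plan does not refine age:

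- The weights are not built to balance time-fixed covariates, because those terms are in the numerator as well.
- The SMD rule looks at bands, so it can show balance while ages inside a band differ. Its remedy, adding an imbalanced covariate to the outcome model, is already used up for age.
- In the 18–49 subgroup the banded covariate is constant, so that estimate has no direct age adjustment.

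All-cause pneumonia has most at stake. Protocol 9.5 hypothesizes a VE of only 5% to 15% and expects more than 20,000 events in every scenario, so a bias of a few points is comparable with the sampling error.

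**Working it through.** **Band widths.** Entry requires "At least 18 years of age at the time of the first recording of HIV-related" code, so the first band holds 49 − 18 + 1 = 32 whole years. The next two hold 15 and 10, and the last is open.

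**The plan's own precision, as a scale.** Protocol Table 3 (all-cause pneumonia, VE 5%, 4% annual censoring, 36 months) gives 23,370 events and a 95% CI of 1% to 9%. Use SE(log HR) = √(1/d₁ + 1/d₀). The vaccinated share of events is not stated; assume 13%, so d₁ = 3,038 and d₀ = 20,332. Then SE = 0.0195 and the limits are 1 − 0.95·exp(±1.96 × 0.0195) = 1.3% and 8.6%, which round to the stated interval. The stated half-width is about 4 points. This figure does not depend on how age is coded.

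**Bias inside a band.** The documents give no age slopes, so these inputs are assumptions: ages uniform within band, 15% of time vaccinated, and uptake v(a) and outcome hazard h(a) log-linear in age. The factor on the HR is the mean of h weighted by v, divided by the mean of h weighted by 1 − v.

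| Uptake / hazard per decade | 18–49 | 50–64 | 65–74 |
|---|---|---|---|
| +10% / +20% | 1.0174 | 1.0038 | 1.0017 |
| +20% / +35% | 1.0547 | 1.0120 | 1.0053 |
| +30% / +50% | 1.1061 | 1.0233 | 1.0103 |

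In the middle case the vaccinated in 18–49 are on average 1.8 years older. The within-band SD of a uniform age is 9.23 years, so this is an SMD of about 0.2, twice the SAP threshold, and the banded SMD would not register it.

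**Cohort-wide.** Assume 40% to 70% of the cohort is aged 18–49, with the rest split 80:20 between 50–64 and 65–74 and nobody older. Weight the log factors by each band's share of events. Middle case at 70%:

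- Mean hazards relative to age 18 are 1.654, 3.250 and 4.708.
- Event weights are 0.70 × 1.654 = 1.158, 0.24 × 3.250 = 0.780 and 0.06 × 4.708 = 0.282, so the shares are 0.521, 0.351 and 0.127.
- The log factor is 0.521 × 0.0533 + 0.351 × 0.0119 + 0.127 × 0.0053 = 0.0327, so the HR is multiplied by 1.0332.
- A true VE of 5% reads 1 − 0.95 × 1.0332 = 1.8%.

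| Slopes | HR factor, 40%–70% aged 18–49 | VE 5% reads | VE 15% reads |
|---|---|---|---|
| Low | 1.007–1.012 | 4.3–3.9% | 14.4–14.0% |
| Middle | 1.021–1.033 | 3.0–1.8% | 13.3–12.2% |
| High | 1.036–1.058 | 1.6 to -0.5% | 12.0–10.1% |

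**18–49 subgroup.** Here the single-band factors apply directly: a VE of 5% reads 3.3%, -0.2% or -5.1%.

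**Direction.** With 32% vaccinated, logistic uptake (odds ratio 0.8 to 1.5 per decade) and rate ratios of 1.1 to 1.5 per decade, the 18–49 factor runs from 0.93 to 1.14. If either slope is nil, the factor is 1.

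**IPD.** At VE 7.5% the high-slope factor of 1.058 gives 1 − 0.925 × 1.058 = 2.1%, a shift of about 5 points. The Protocol Table 2 interval (36 months, 4% censoring) is -12% to 25%.

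**The case against.** The best defence is that age is not the only control. Payor (including Medicare), index year, prior pneumonia, hospitalization, smoking, the main chronic diseases, influenza vaccination and physical exams are all adjusted. They will absorb part of the within-band age effect, so the factors above are upper figures for their slopes. This stands.

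There are also partial safeguards. Age is summarized as continuous by vaccination status at the end of baseline (SAP 5.8.9), VE by age group may be estimated, and negative controls are planned. These might reveal a problem, but none refines age in a model. The negative controls are aimed at care-seeking and immune status and cannot identify age as the source, and the bias correction is optional.

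Four stronger readings are tempting, and the documents do not support them:

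- **The 18–49 factors are the bias in the study result.** They apply to one band. If risk rises with age, that band supplies fewer events than persons, and the overall factor is much smaller.
- **VE is understated.** That needs uptake to rise with age within bands. The documents do not say so; if uptake falls with age, VE is overstated.
- **Passing 65 changes vaccine eligibility.** Protocol section 7 shows no such change for this cohort. PCV13 has been recommended to people with HIV since 2012 with no age cut, and the current advice covers both those aged 19–64 with HIV and everyone aged 65 or over.
- **Age must be updated during follow-up.** The weight models run on time since index. Attained age is baseline age plus that time, so a linear term gives the same fit as baseline age.

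**Conclusion.** The coding gap is certain from the text: four bands, one of 32 years, with age in years held but not modelled, and no planned step that refines it. Within-band age confounding is therefore not fully removed. How much remains is not known. Under the assumed slopes the cohort-wide HR is inflated by about 1% to 6% before absorption by other covariates; the sign reverses if uptake falls with age. For all-cause pneumonia at a VE of 5%, the middle and high cases move the estimate by about 2 to 5.5 points, similar to the planned 36-month half-width of about 4. For IPD the shift is small beside the interval. The 18–49 subgroup is the most exposed. This is not a fatal flaw, but it is an avoidable one that should be closed because the remedy is nearly free.

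**What to change.** In SAP Table 5.3, change the covariate role of age to baseline age in years, entered as a restricted cubic spline with prespecified knots. Use it in the weight numerator, the weight denominator and the Cox-MSM, including within the age subgroups. Build the spline as numeric basis columns beforehand, since SAP 7.2.1 requires numeric variables for the weighting function. Add the SMD of continuous age, overall and within bands, to SAP 5.8.5. Keep the bands for tables and subgroup definitions, and align Protocol Table 1. If the banded model has to stay primary, prespecify the spline model as a sensitivity analysis for every outcome.

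The cost is SAP wording and a few parameters in a cohort of about 175,000. No new data are needed, and the planned size and precision do not change.
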